6.2.4.1. Main Analysis

- Estimand strategy: Secondary Estimand ([Section 2.2.2](#)).
- Analysis set: FAS ([Section 4](#)).

- Analysis methodology: Change from baseline in velocity will be analyzed using an MMRM approach ([Section 5.2.1.1](#)) including visits through Week 52 where NSAA is assessed (ie, Weeks 9, 18, 35, 52) with additional fixed effects for Baseline velocity (continuous variable), Screening age covariate (continuous variable), Baseline by visit interaction, and Screening age covariate by visit interaction.
- Intercurrent events and missing data: All available data in the reporting period will be included. The intercurrent events and missing data will be handled as described in [Section 2.2.2](#)
- N, mean, SD, median, Q1, Q3, minimum, and maximum at Baseline and all visits through Week 52 where NSAA is assessed for observed velocities of the endpoints and changes from baseline in velocity will be provided for fordadistrogene movaparvovec and placebo.
- The fordadistrogene movaparvovec and placebo LS means, standard error of each LS mean, and 95% CIs for the LS means along with the difference between the LS means (fordadistrogene movaparvovec minus placebo) and the corresponding standard error, two-sided p-value, and 95% CI will be provided for change from baseline for all visits through Week 52 where NSAA is assessed.

Graphical displays:

- The fordadistrogene movaparvovec and placebo LS means, and 95% CIs for the LS means for each visit will be displayed graphically.

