6.5.1. Screening Age Strata

The following endpoints will be evaluated by two screening age strata (<6 years and ≥ 6 years):

- Change from Baseline at Week 52 in the NSAA total score.
- Change from Baseline at Week 52 in the 10 meter run/walk test velocity.
- Change from Baseline at Week 52 in the rise from floor velocity.
- Number of skills gained at Week 52 based on the individual items of the NSAA.
- Number of skills either improved or maintained at Week 52 based on the individual items of the NSAA.
- Change from Baseline at Week 52 in the 95th percentile of cadence.

The age strata at screening (Randomization Group) collected in the clinical database will be used for subset analysis.

- Analysis set: FAS ([Section 4](#)).
- Analysis methodology:
 - The analysis methods for the main analysis of primary endpoint in [Section 6.1](#) and the secondary endpoints in [Section 6.2](#) will be applied for the subset analysis, where the model will be handled in a different way as below:
 1. Analysis for the endpoints change from Baseline at Week 52 in the NSAA total score, 10 meter run/walk test velocity, rise from floor velocity, and 95th percentile of cadence.

- For each Screening age strata separately, change from baseline will be analyzed using an MMRM approach ([Section 5.2.1.1](#)) including visits through Week 52 with additional fixed effects for Baseline(continuous variable), and Baseline by visit interaction.

For each Screening age strata, estimates of the mean changes from Baseline, standard error of each LS mean, and 95% confidence intervals for fordadistrogene movaparvovec and placebo will be provided for each visit along with the mean treatment group difference and the corresponding standard error, two-sided p-value, and two-sided 95% confidence interval for the mean difference at each visit.

- Change from baseline will be analyzed using an MMRM approach ([Section 5.2.1.1](#)) including visits through Week 52 with additional fixed effects for Baseline (continuous variable), Baseline by visit interaction, Screening age strata (binary variable), Screening age strata by visit interaction, and Screening age strata by treatment group interaction.

The p-value for the Screening age strata interaction term will be provided.

2. Analysis for endpoints number of skills gained and number of skills either improved or maintained at Week 52

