Change from Baseline at Week 52 in the 10 meter run/walk velocity	Summary	FAS	All available data excluding the data from the particular rater(s) with potential data quality issues will be included Missing data will not be imputed	N/A
Change from Baseline at Week 52 in the 10 meter run/walk velocity	Sensitivity analysis Plot of LS means and 95% CIs	FAS	All available data excluding the data from the particular rater(s) with potential data quality issues will be included Missing data will not be explicitly imputed	MMRM with additional fixed effects for Baseline, Screening age covariate, Baseline by visit interaction, and Screening age covariate by visit interaction
Change from Baseline at Week 52 in the 10 meter run/walk velocity	Screening age strata subset Summary	FAS	All available data will be included Missing data will not be imputed	Not applicable (N/A)
Change from Baseline at Week 52 in the 10 meter run/walk velocity	Screening age strata subset	FAS	All available data will be included Missing data will not be explicitly imputed	For each Screening age strata separately, MMRM with additional fixed effects for Baseline NSAA total score, and Baseline NSAA total score by visit interaction.
Change from Baseline at Week 52 in the 10 meter run/walk velocity	Screening age strata subset The p-value for the Screening age strata interaction term	FAS	All available data will be included Missing data will not be explicitly imputed	NSAA main analysis (MMRM) subset on Screening age strata and MMRM with additional fixed effects for Baseline NSAA total score, Baseline NSAA total score by visit interaction, Screening age strata, Screening age strata by visit interaction, and Screening age strata by treatment group interaction.
Change from Baseline at Week 52 in the 10 meter run/walk velocity	Baseline NSAA total score subset Summary	FAS	All available data will be included Missing data will not be explicitly imputed	Not applicable (N/A)

Endpoint	Analysis Type	Population	Data Inclusion and Rules for Handling Intercurrent Events and Missing Data	Analysis Model

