Change from Baseline at Week 52 in the rise from floor velocity	Screening age strata subset Summary	FAS	All available data will be included Missing data will not be imputed	Not applicable (N/A)
Change from Baseline at Week 52 in the rise from floor velocity	Screening age strata subset	FAS	All available data will be included Missing data will not be explicitly imputed	For each Screening age strata separately, MMRM with additional fixed effects for Baseline, and Baseline by visit interaction.
Change from Baseline at Week 52 in the rise from floor velocity	Screening age strata subset The p-value for the Screening age strata interaction term	FAS	All available data will be included Missing data will not be explicitly imputed	NSAA main analysis (MMRM) subset on Screening age strata and MMRM with additional fixed effects for Baseline , Baseline by visit interaction, Screening age strata, Screening age strata by visit interaction, and Screening age strata by treatment group interaction.
Change from Baseline at Week 52 in the rise from floor velocity	Baseline NSAA total score subset Summary	FAS	All available data will be included Missing data will not be explicitly imputed	Not applicable (N/A)
Change from Baseline at Week 52 in the rise from floor velocity	Baseline NSAA total score subset	FAS	All available data will be included Missing data will not be explicitly imputed	For each baseline NSAA total score strata separately, MMRM with fixed effects for treatment group, visit, and treatment group by visit interaction with additional fixed effects for screening age covariate and screening age by visit interaction.

Endpoint	Analysis Type	Population	Data Inclusion and Rules for Handling Intercurrent Events and Missing Data	Analysis Model
Change from Baseline at Week 52 in the rise from floor velocity	Geographic region subset Summary	FAS	All available data will be included Missing data will not be explicitly imputed	Not applicable (N/A)
Change from Baseline at Week 52 in the rise from floor velocity	Geographic region subset	FAS	All available data will be included Missing data will not be explicitly imputed	MMRM with treatment group, visit, and treatment group by visit interaction with additional fixed effects for baseline, baseline by visit interaction, screening age covariate, and screening age by visit interaction
PODCI				

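### In Appendix 1, the two age-stratum model rows for 10 meter run/walk velocity adjust for Baseline NSAA total score, whereas Section 6.5.1 calls for the endpoint's own baseline

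*SAP*

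**What the plan says.** **Section 6.5.1** sets out the age-stratum analyses. One block of model text covers four continuous endpoints: "Analysis for the endpoints change from Baseline at Week 52 in the NSAA total score, 10 meter run/walk test velocity, rise from floor velocity", and the 95th percentile of cadence. Within each stratum the MMRM is fitted "with additional fixed effects for Baseline(continuous variable), and Baseline by visit interaction". The interaction model is fitted "with additional fixed effects for Baseline (continuous variable), Baseline by visit interaction, Screening age strata (binary variable"), plus stratum by visit and stratum by treatment. The section says that the methods of the main analyses carry over, apart from the changes it lists.

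**Section 3.4.1** defines Baseline for secondary endpoints as the last non-missing pre-dose assessment. It defines Baseline NSAA total score separately, for the primary endpoint.

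**Section 6.2.4.1**, the main analysis of both velocities, is explicit: "with additional fixed effects for Baseline velocity (continuous variable), Screening age covariate (continuous variable").

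**Appendix 1, 10 meter run/walk velocity, age-stratum rows**, differs. The within-stratum row reads "For each Screening age strata separately, MMRM with additional fixed effects for Baseline NSAA total score, and Baseline NSAA total score by visit interaction". The interaction row reads "MMRM with additional fixed effects for Baseline NSAA total score, Baseline NSAA total score by visit interaction, Screening age strata", followed by the stratum interactions.

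**Appendix 1, rise from floor velocity, same analysis**, reads "For each Screening age strata separately, MMRM with additional fixed effects for Baseline, and Baseline by visit interaction".

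**The concern.** Two current parts of the SAP specify different covariates for the same analysis. Under Section 6.5.1, change in velocity is adjusted for baseline velocity. Under Appendix 1, it is adjusted for a different instrument's baseline and has no baseline velocity term. The SAP has no precedence rule, and Appendix 1 is the more endpoint-specific of the two, so a programmer could reasonably follow either.

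What is at stake is the age-subgroup output for the endpoint listed first in the fixed sequence of Section 5.1. Age is also the stratification factor, so these subgroup results are likely to be read closely. The strata are small and allocation is 2:1, so a chance difference between arms in baseline velocity is plausible. Baseline NSAA would absorb only part of it. If the wording is not settled before unblinding, the choice of model could be made with results in view.

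**Working it through.** **1. Is the conflict real?** The baseline covariate named in each place is:

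| Place in the SAP | Baseline covariate |
|---|---|
| 6.5.1, within stratum and interaction (four endpoints) | Baseline |
| 6.2.4.1, main analysis of the velocities | Baseline velocity |
| Appendix 1, 10 meter: main, rater sensitivity, region | Baseline |
| Appendix 1, 10 meter: age stratum, both model rows | **Baseline NSAA total score** |
| Appendix 1, rise from floor: age stratum, both model rows | Baseline |
| Appendix 1, cadence: age-stratum interaction row | Baseline |
| Appendix 1, NSAA total score: age stratum, both model rows | Baseline NSAA total score (its own baseline) |

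The two 10 meter rows are the only ones that name another endpoint's baseline. Their wording matches the NSAA total score rows, where it is right, so it was probably carried over from there. This is current text, not the amendment history.

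**2. How much could precision change?** The plan states no figure to reproduce and gives no correlations, so every correlation here is an assumption. Take a single time point with equal SDs at baseline and Week 52, scaled to 1. Let ρ be the correlation of baseline with Week 52 velocity, and r0 and r1 the correlations of baseline NSAA with baseline and Week 52 velocity. The residual variance of change is:

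- adjusting for baseline velocity: 1 − ρ²
- adjusting for baseline NSAA: 2(1 − ρ) − (r1 − r0)²

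The SE ratio (NSAA-adjusted to velocity-adjusted) is the square root of the second over the first. Two examples:

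- ρ = 0.6, r0 = r1 = 0.5: √(0.80/0.64) = 1.118
- ρ = 0.9, r0 = 0.7, r1 = 0.6: √(0.19/0.19) = 1.000

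| ρ | r0/r1 = 0.5/0.5 | 0.7/0.6 | 0.8/0.7 |
|---|---|---|---|
| 0.6 | 1.118 | 1.111 | 1.111 |
| 0.7 | 1.085 | 1.076 | 1.076 |
| 0.8 | 1.054 | 1.041 | 1.041 |
| 0.9 | 1.026 | 1.000 | 1.000 |

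The penalty is about 0% to 12%.

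**3. What happens to a chance baseline imbalance?** With NSAA in the model, change still depends on baseline velocity with slope (ρ − r0·r1)/(1 − r0²) − 1. Over the same grid this runs from −0.06 (ρ = 0.9, 0.7/0.6: 0.48/0.51 − 1) to −0.89 (ρ = 0.6, 0.8/0.7: 0.04/0.36 − 1).

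Section 2.3 caps either stratum at 55%. Applied to 99 boys, that gives strata of about 45 to 54, or 30 v 15 to 36 v 18 at 2:1. The standard error of a chance difference in mean baseline velocity is √(1/30 + 1/15) = 0.32 SD, or √(1/36 + 1/18) = 0.29 SD. The part that NSAA does not explain would pass into the estimate in proportion to the slope above. This is the effect of step 2 seen from a realised imbalance, not a second penalty.

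**The case against.** The strongest reply is that these are miscopied cells in a table headed as a summary. Section 6.5.1 holds the detailed method and is clear, so a programmer working from it would fit the intended model. That is likely, but the SAP does not say that Section 6 prevails, so the cells still need correcting.

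The subgroup models also do not share one covariate set anyway. The age-stratum models drop continuous screening age. The Baseline NSAA subgroup model in Section 6.5.2 has no baseline velocity term, consistently in body and appendix. This reply stands against any complaint that the estimates would not be comparable with the main analysis. It does not answer the direct contradiction between two texts, or the mismatch with rise from floor.

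Three stronger readings are tempting, and the documents do not support them:

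- *The error-controlled test is compromised.* It is not. That test uses the main analysis, where Section 6.2.4.1 and Appendix 1 agree, and no decision rule in the SAP depends on the age-subgroup results.
- *Omitting baseline velocity lets regression to the mean bias the treatment difference.* Regression to the mean acts on both randomised arms alike, and randomisation is stratified by this same age split. Either covariate leaves the difference unbiased in expectation. What remains is precision and sensitivity to chance imbalance.
- *Some precision must be lost.* A positive minimum follows only if NSAA relates to change solely through baseline velocity. If NSAA has prognostic value of its own, the loss can fall to nil, as the grid shows.

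**Conclusion.** The contradiction holds. The two 10 meter run/walk age-stratum model rows of Appendix 1 name a covariate that conflicts with Section 6.5.1 as read with Sections 3.4.1 and 6.2.4.1. The two versions can give different subgroup estimates, confidence intervals and interaction p-values.

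The effect is limited. Following Appendix 1 would leave the standard error about 0% to 12% larger, and would leave unadjusted the part of any baseline-velocity imbalance that NSAA does not explain. Those figures rest on assumed correlations, equal SDs and a single-time-point approximation to the MMRM. The textual conflict does not depend on them. The primary analysis, the main analysis of this endpoint and the fixed-sequence test are unaffected.

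**What to change.** In Appendix 1, under 10 meter run/walk velocity, amend the within-stratum row and the interaction row of the age-stratum analysis. In each, replace Baseline NSAA total score with Baseline 10 meter run/walk velocity, both as a main term and in the by-visit interaction. Both rows then match Sections 6.5.1 and 6.2.4.1. A statement that Section 6.5.1 governs would also remove the ambiguity.

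The cost is two table cells, with no change to data collection, sample size or the confirmatory analyses. It is best done before unblinding.

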Appendix 2. Data Derivation Details

Appendix 2.1. Definition and Use of Analysis Visit Windows in Reporting

The below analysis windows will be used for the efficacy parameters. If multiple values are observed within a window, the value closest (and prior) to the target day will be included in the analysis. If multiple values are observed within the same day, the worst value will be included in the analysis.

Efficacy Parameter	Visit label	Target day ¹	Window lower limit	Window upper limit ²
NSAA, actigraphy, ankle range of motion	Week 9	60	50	70
	Week 18	120	100	140
	Week 35	240	200	280
	Week 52	360	300	390
CK levels	Week 1, Day 4	4	2	7
	Week 2, Day 14	14	11	17
	Week 3	21	18	24
	Week 4	28	25	31
	Week 5	34	32	41
	Week 7	48	42	54
	Week 9	60	55	67
	Week 11	74	68	82
	Week 13	90	83	105
	Week 18	120	106	140
	Week 35	240	200	280
Week 52	360	300	390	
Muscle biopsy	Week 52	360	300	390
%pFVC, EQ-5D-Y (proxy), EQ-5D-5L (caregivers of participants)	Week 52	360	300	390
PODCI	Week 35	240	200	280
	Week 52	360	300	390
1. Relative to Day 1 (day of IP administration) 2. If Year 2 Day 1 IP is administered after Day 390, the upper limit for the Week 52 window will be Day 390. If Year 2 Day 1 IP is administered on or prior to Day 390, the upper limit for the Week 52 window will be one day before the day of Year 2 Day 1 IP administration.				

The below analysis windows will be used for the immunogenicity parameters. If multiple values are observed within a window, the value closest (and prior) to the target day will be included in the analysis.

Immunogenicity Parameter	Visit label	Target day ¹	Window lower limit	Window upper limit ²
ADA to mini-dystrophin	Week 2, Day 14	14	2	17
	Week 3	21	18	24
	Week 4	28	25	31
	Week 5	34	32	41
	Week 18	120	100	140
	Week 52	360	300	390

ADA to AAV9	Week 5	34	20	48
	Week 18	120	100	140
	Week 52	360	300	390
NAbs	Week 5	34	20	48
	Week 52	360	300	390
T cell response	Week 9	60	50	70
1. Relative to Day 1 (day of IP administration) 2. If Year 2 Day 1 IP is administered after Day 390, the upper limit for the Week 52 window will be Day 390. If Year 2 Day 1 IP is administered on or prior to Day 390, the upper limit for the Week 52 window will be one day before the day of Year 2 Day 1 IP administration.				

The below analysis windows will be used for the safety parameters. If multiple values are observed within a window, the worst value will be included in the analysis.

Safety Parameter	Visit label	Target day ¹	Window lower limit	Window upper limit ²
CK levels (higher values are worse)	Week 1, Day 4	4	2	10
	Week 2, Day 14	14	11	17
	Week 3	21	18	24
	Week 4	28	25	31
	Week 5	34	32	41
	Week 7	48	42	54
	Week 9	60	55	67
	Week 11	74	68	82
	Week 13	90	83	105
	Week 18	120	106	180
	Week 35	240	181	300
	Week 52	360	301	390
Creatinine (higher values are worse)	Week 1, Day 2	2	2	3
	Week 1, Day 4	4	4	5
	Week 1, Day 6	6	6	6
	Week 1, Day 7	7	7	7
	Week 2, Day 8	8	8	8
	Week 2, Day 9	9	9	9
	Week 2, Day 10	10	10	12
	Week 2, Day 14	14	13	17
	Week 3	21	18	27
	Week 5	34	28	41
	Week 7	48	42	54
	Week 9	60	55	67
	Week 11	74	68	82
	Week 13	90	83	105
	Week 18	120	106	180
	Week 35	240	181	300
Week 52	360	301	390	
GLDH levels (higher values are worse)	Week 1, Day 2	2	2	3
	Week 1, Day 4	4	4	6
	Week 2, Day 9	9	7	11
	Week 2, Day 14	14	12	17
	Week 3	21	18	24
	Week 4	28	25	31

Safety Parameter	Visit label	Target day ¹	Window lower limit	Window upper limit ²
	Week 5	34	32	41
	Week 7	48	42	54
	Week 9	60	55	67
	Week 11	74	68	82
	Week 13	90	83	105
	Week 18	120	106	180
	Week 35	240	181	300
	Week 52	360	301	390
Platelets (lower values are worse)	Week 1 Day 2	2	2	3
	Week 1, Day 4	4	4	5
	Week 1, Day 6	6	6	6
	Week 1, Day 7	7	7	7
	Week 2, Day 8	8	8	8
	Week 2, Day 9	9	9	9
	Week 2, Day 10	10	10	12
	Week 2, Day 14	14	13	17
	Week 3	21	18	27
	Week 5	34	28	47
	Week 9	60	48	75
	Week 13	90	76	105
	Week 18	120	106	180
	Week 35	240	181	300
	Week 52	360	301	390
	GGT levels (higher values are worse)	Week 1 Day 2	2	2
Week 1, Day 4		4	4	9
Week 2, Day 14		14	10	17
Week 3		21	18	27
Week 5		34	28	41
Week 7		48	42	54
Week 9		60	55	67
Week 11		74	68	82
Week 13		90	83	105
Week 18		120	106	180
Week 35		240	181	300
Week 52		360	301	390
C3, C4 levels (lower values are worse)	Week 1, Day 2	2	2	3
	Week 1, Day 4	4	4	5
	Week 1, Day 6	6	6	6
	Week 1, Day 7	7	7	7
	Week 2, Day 8	8	8	8
	Week 2, Day 9	9	9	9
	Week 2, Day 10	10	10	12
	Week 2, Day 14	14	13	17
	Week 3	21	18	27
	Week 5	34	28	47
Cardiac Troponin I levels (higher values are worse)	Week 1 Day 2	2	2	3
	Week 1, Day 4	4	4	5
	Week 1, Day 6	6	6	7
	Week 2, Day 8	8	8	9
	Week 2, Day 10	10	10	12
	Week 2, Day 14	14	13	17

Safety Parameter	Visit label	Target day ¹	Window lower limit	Window upper limit ²
	Week 3	21	18	24
	Week 4	28	25	31
	Week 5	34	32	37
	Week 6	42	38	45
	Week 7	48	46	54
	Week 9	60	55	67
	Week 11	74	68	82
	Week 13	90	83	105
	Week 18	120	106	240
	Week 52	360	241	390
Vital Signs ^a	Week 1 Day 1	1	1	1
	Week 1 Day 2	2	2	3
	Week 1, Day 4	4	4	5
	Week 1, Day 6	6	6	6
	Week 1, Day 7	7	7	7
	Week 2, Day 8	8	8	8
	Week 2, Day 9	9	9	9
	Week 2, Day 10	10	10	12
	Week 2, Day 14	14	13	17
	Week 3	21	18	27
	Week 5	34	28	47
	Week 9	60	48	75
	Week 13	90	76	105
	Week 18	120	106	180
	Week 35	240	181	300
		Week 52	360	301
ECGs ^b	Week 1 Day 1	1	1	2
	Week 1, Day 7	7	3	9
	Week 2, Day 14	14	10	17
	Week 3	21	18	27
	Week 5	34	28	47
	Week 9	60	48	75
	Week 13	90	76	105
	Week 18	120	106	180
	Week 35	240	181	300
	Week 52	360	301	390

a: If multiple values are observed within a window, the average of all those values will be used.

b: For quantitative values, if multiple values are observed within a window, the average of all those values will be used. For qualitative values, if multiple visits are windowed, the abnormality flag will be used in generating the incidence of abnormality.

The below analysis windows will be used for viral vector shedding. If multiple values are observed within a window, the largest value will be included in the analysis.

Parameter	Visit label	Target day ¹	Window lower limit	Window upper limit
Viral vector shedding (Whole blood)	Week 1, Day 2	2	2	2
	Week 1, Day 4	4	3	11
	Week 3	21	12	40
	Week 9	60	41	75

Parameter	Visit label	Target day ¹	Window lower limit	Window upper limit
	Week 13	90	76	105
	Week 18	120	106	180
	Week 35	240	181	300
	Week 52	360	301	390
Viral vector shedding (urine and saliva)	Week 1, Day 1	1	1	1
	Week 1, Day 2	2	2	2
	Week 1, Day 4	4	3	5
	Week 1, Day 7	7	6	8
	Week 2, Day 10	10	9	11
	Week 2, Day 14	14	12	16
	Week 3	21	17	25
	Week 5	34	26	47
	Week 9	60	48	75
	Week 13	90	76	105
	Week 18	120	106	180
	Week 35	240	181	300
	Week 52	360	301	390
1. Relative to Day 1 (day of IP administration) 2. If Year 2 Day 1 IP is administered after Day 390, the upper limit for the Week 52 window will be Day 390. If Year 2 Day 1 IP is administered on or prior to Day 390, the upper limit for the Week 52 window will be one day before the day of Year 2 Day 1 IP administration.				

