3.5. Safety Endpoints

For safety endpoints, unless otherwise specified, Baseline is defined as the last non-missing assessment collected prior to Day 1 (Year 1 Day 1) IP administration. For vital signs, baseline is defined as the assessment collected prior to dosing (0 minutes) on Day 1.

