6.7.3. Vital Signs (including body weight)

Observed values and changes from baseline in vital sign parameters will be summarized descriptively for fordadistrogene movaparvovec and placebo by visit. If there are multiple records at any timepoint after the start of infusion on Day 1, the average will be included in the analysis.

Categorical tables including post-baseline values, maximum increases (in blood pressure and pulse rate), and maximum decreases (in blood pressure and pulse rate) will be provided. Additionally, categorical tables will also be provided for the first 7 days of follow-up and the first 30 days of follow-up.

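### Read literally, the Day 1 window for vital signs averages the pre-dose baseline into the value compared with it, at odds with Section 6.7.3; the ECG Day 1 window does not exclude pre-dose records either

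*SAP*

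**What the plan says.** **Baseline.** SAP Section 3.5 gives safety endpoints a general rule: "Baseline is defined as the last non-missing assessment collected prior to Day 1 (Year 1 Day 1) IP administration". It then gives vital signs their own rule: "For vital signs, baseline is defined as the assessment collected prior to dosing (0 minutes) on Day 1".

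**Windows.** In the safety table of Appendix 2.1, the limits are calendar days counted from the day of dosing. The first vital-sign row (label, target, lower limit, upper limit) is "Week 1 Day 1 1 1 1", so it covers all of Day 1. The first ECG row is "Week 1 Day 1 1 1 2", so it covers Days 1 and 2. Neither row is split at the time of dosing.

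**Multiple values.** Footnote a, for vital signs: "If multiple values are observed within a window, the average of all those values will be used". Footnote b, for ECG: "For quantitative values, if multiple values are observed within a window, the average of all those values will be used".

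**Analysis sections.** Section 6.7.3 summarizes vital signs as observed values and changes from baseline by visit, and adds: "If there are multiple records at any timepoint after the start of infusion on Day 1, the average will be included in the analysis". Section 6.7.4 summarizes ECG changes from baseline by visit. It has no averaging rule and does not distinguish pre-dose from post-dose records.

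**Reporting period.** Section 2.3.2 starts the reporting period on the day of dosing, so it does not remove pre-dose records of that day.

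**The concern.** A post-baseline visit value should not contain the baseline it is compared with. When it does, the change is pulled towards zero whatever the data show. The infusion day is when an acute effect on blood pressure, pulse or temperature would be expected to appear, so the direction of the error is unhelpful in a safety table.

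There is also a problem of reproducibility. Footnote a and Section 6.7.3 both govern Day 1 vital signs, but they differ in scope (all of Day 1, or only records after the infusion starts) and in unit (the whole window, or a timepoint). Two programmers could each follow the SAP and produce different Day 1 tables from the same data.

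**Working it through.** The SAP states no figure on this point, so there is none to reproduce. The check is a reading of the rules followed by simple algebra.

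**Step 1. Does the vital-sign baseline fall in the window?** By Section 3.5 it is dated Day 1. By Appendix 2.1 the window is Day 1 to Day 1. Neither footnote a nor Section 2.3.2 removes it. Under the literal rule it is always inside.

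**Step 2. Does the rest of the table have this problem?** No. Every laboratory parameter in the safety table has a first window opening on Day 2, so a Day 1 pre-dose sample cannot enter a post-baseline visit. Only vital signs and ECG open on Day 1, so only they need a rule separating pre-dose from post-dose records.

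**Step 3. Size for vital signs if footnote a is followed.** Let B be the baseline reading, k the number of readings after the start of infusion, and D their mean change from B.

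- Window mean = [B + k(B + D)] / (k + 1) = B + D·k/(k + 1)
- Reported change = window mean − B = D·k/(k + 1)
- Share lost = 1/(k + 1)

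The SAP does not give k, so the values below are assumptions.

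| k | Share retained | Share lost | Reported change if D = 10 units |
|---|---|---|---|
| 1 | 0.500 | 0.500 | 5.00 |
| 2 | 0.667 | 0.333 | 6.67 |
| 4 | 0.800 | 0.200 | 8.00 |
| 6 | 0.857 | 0.143 | 8.57 |
| 8 | 0.889 | 0.111 | 8.89 |
| 10 | 0.909 | 0.091 | 9.09 |

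If k is the same in both arms, the difference between arms shrinks by the same factor. If k differs between arms, there is no common factor.

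**Step 4. Size if Section 6.7.3 is followed.** Only readings after the start of infusion are averaged, so the reported change is D and the loss is zero. If both rules were applied in turn (replicates averaged within a timepoint, then timepoints averaged within the window), the Step 3 formula returns, with k counting post-start timepoints.

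**Step 5. ECG.** The baseline is the last non-missing ECG before dosing.

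- If it was recorded on Day 1, it lies in the Day 1–2 window, footnote b averages it in, and the Step 3 formula applies, with k counting the post-start ECGs in that window.
- If it was recorded earlier, it lies outside the window and the loss is zero.

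The SAP does not say which case holds.

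**The case against.** The best defence is that a specific rule overrides a general one. Footnote a covers all 16 vital-sign windows from Day 1 to Week 52, whereas Section 6.7.3 speaks of Day 1 in particular. Section 3.5 has already set the pre-dose record apart as baseline. Read together, these passages keep baseline out of the average and nothing is lost. This is a fair reading and is why zero belongs in the range. It does not close the point, because the SAP never states that precedence. The change history does not settle it either: the entry on multiple records at a timepoint dates from version 4, while the algorithm for multiple values within a window was clarified in version 9, the current one. A programmer could reasonably take the appendix as the later instruction.

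A second defence is that acute effects have other displays. Section 6.7.3 plans categorical tables of post-baseline values and of maximum increases and decreases in blood pressure and pulse, including for the first 7 days. Section 6.7.4 and Appendix 2.2.2 classify ECG findings by maximum values. Section 6.7.1 plans summaries of adverse events of interest, with peri-infusion categories. This limits the harm and stands. Two gaps remain: the SAP does not say whether the categorical tables use unaveraged records, and the maximum-change tables do not cover temperature.

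A reader might also infer that the ECG change is diluted in the same automatic way and that footnote b contradicts Section 6.7.3. The SAP supports neither. The ECG baseline need not fall on Day 1, Section 6.7.3 concerns vital signs only, and Section 6.7.4 contains no averaging rule that footnote b could contradict.

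**Conclusion.** For vital signs the point holds as an unresolved conflict between Appendix 2.1 footnote a and Section 6.7.3. Under footnote a as written, the baseline is part of the Day 1 value and the reported change is too small by 1/(k+1): half for one post-start reading, about a tenth for ten. Under Section 6.7.3 nothing is lost. It would be too strong to say that the Day 1 change is diluted by construction, because that assumes footnote a prevails. The size also rests on k, which is assumed, and on a single pre-dose reading per participant.

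For ECG there is a gap, not a contradiction: nothing keeps a pre-dose record out of the Day 1–2 window, and whether that matters depends on when the baseline ECG was taken.

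The consequence is confined to descriptive by-visit safety summaries. No hypothesis test, primary endpoint or type I error rate is touched. This is a minor point, worth correcting because the correction is easy.

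**What to change.** In Appendix 2.1, add one clause to footnotes a and b: the Week 1 Day 1 window uses only records taken after the start of infusion and excludes the record flagged as baseline.

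For vital signs, also state whether multiple Day 1 records are averaged within each timepoint or across the whole window, and word footnote a and Section 6.7.3 the same way. For ECG, the clause in footnote b is enough; if the baseline ECG was taken before Day 1, it changes nothing.

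The cost is a few words in two footnotes and a matching filter in the programs for the Day 1 tables. It needs no new data and leaves every efficacy analysis unchanged.
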